**NCT Number: NCT04373421**

**Study Protocol, and Statistical Analysis Plan**

**Study Protocol**

This randomized double-blind clinical trial will be conducted in Ankara Yıldırım Beyazıt University Oral and Maxillofacial Surgery Clinic and Van Yüzüncü Yıl University. Ethical approval of the study was obtained from Van Yüzüncü Yıl University Faculty of Medicine Clinical Research Ethics Committee in accordance with the Declaration of Helsinki (Decision Date and Number: 01.08.2018-08). Signed informed consent will be obtained from all patients.

90 healthy individuals who need third molar surgery will be included in this study. Inclusion criteria: Between 18-40 years of age, having asymptomatic unilateral mandibular impacted third molars (mesioangular) with similar angular positions according to the Winter classification and a similar degree of impaction according to Pell and Gregory's classification (class II, level B). Patients with a history of smoking, drug use, and pericoronitis associated with the lower third molar will be excluded. Pregnant and lactating women, patients with periodontal problems in the adjacent second molars (ie, increased periodontal depth, gingival recession), or patients without adjacent second molars on the operative side will also be excluded.

The predictive variable will be the type of mouthwash used in the study (St. John's wort oil and olive oil) and the control (chlorhexidine gluconate + benzylamine hydrochloride) groups. The outcome variable will be patient-reported pain and difficulty in jaw function, trismus, facial swelling, the number of analgesics used in the first postoperative week, and postoperative periodontal status.

All patients included will be randomly divided into 3 groups. St. John's wort oil will be given; Extra virgin olive oil will be given to the patients in the second group, and the mouthwash containing chlorhexidine gluconate and benzylamine hydrochloride will be given to the patients in the third group. Randomization will be performed by permutation method in MedCalc 11.5.1 software (MedCalc Software Inc, Ostend, Belgium). Three types of mouthwash will be given to the clinicians without notifying the surgical procedure or

postoperative controls, which are individually placed in boxes by the assistant personnel categorized as group 1, group 2 and group 3.

All procedures will be performed by the same surgeons in each center, using a standard protocol in each medical center. Local anesthesia will be administered using 0.01 mg / ml epinephrine and 2 ml articaine hydrochloride 40 mg / ml (Maxicaine Fort, VEM Drug, Istanbul, Turkey). Horizontal incision no. 15 scalpel blades and full thickness mucoperiosteal flaps will be removed. In all surgical procedures, bone removal and / or tooth cutting will be performed under copious irrigation. Following extraction, the granulation tissues will be removed and the post-extraction cavity washed with sterile 0.9% saline solution. After the bleeding is controlled, the mucoperiosteal flap will be repositioned with a 3.0 silk suture. Paracetamol (Parol® 500 mg, Atabay Kimya Sanayi, Istanbul, Turkey) was prescribed to the patients to use when necessary, with a maximum of 4 doses per day after surgery. Patients will be instructed to maintain a gentle diet for the first 24 hours and to avoid mouthwashing, brushing, and flossing. In addition, they will be asked to rinse their mouths with 15 ml of mouthwash 3 times a day for 30 seconds and continue until the 7th day after surgery.

The maximum mouth opening (MMO) will be measured in millimeters with a caliper from the incisal edge of the right upper and lower incisors. To evaluate the trismus, the percentage difference in MMO at the postoperative period (B), subtract the preoperative measurement (A) from the postoperative measurement, and then divide the preoperative measurement (A) and multiply by 100 (percentage difference =  $[B - A] / B \times 100$ ) . Facial swelling will be assessed using a thread and a millimeter ruler and five additional measurements will be made: distance I (from mandible to labial commissure); distance II (from angle of mandible to nose border) distance III (from the angle of the mandible to the outer corner of the eye); distance IV (from angle of mandible to tragus) and distance V (from mandible to soft pogonion). To evaluate the changes in the above distances in the postoperative period, the percentage of facial swelling will be calculated by subtracting the preoperative measurement from the postoperative measurement and then dividing it by the preoperative measurement and multiplying by 100.

A 7-day planned pain diary will be given to patients to evaluate postoperative pain and jaw function. To record the level of pain, patients will be instructed to grade on 100 mm visual analog scales (VAS) where 0 indicates no pain and 100 indicates the worst pain imaginable. To assess the difficulty in jaw function, patients will be asked to rate it at 100 mm VAS, where 0 indicates no limitation and 100 indicates severe limitation. They will also be asked to note how many painkillers they take per day. Patients will be evaluated for facial

swelling and trismus on postoperative 1st, 3rd and 7th days. In addition, complications such as alveolitis and infection will be recorded observationally.

All clinical periodontal assessments were to be measured by a blind examiner and mesio-buccal, mid-buccal, disto-buccal and disto-lingual were selected around adjacent second molar measurements for four regions. The plaque index defined by Silness and Loe will be used to evaluate patients' dental plaque status. Plaque thickness on the third gum of the teeth will be evaluated. The scores for each unit will then be summed up and divided by the total number of areas evaluated to arrive at the plaque index. The gingival bleeding index, introduced by Ainamo and Bay, will be used in the assessment of patients' gingivitis. The second molar will be probed gently with a periodontal probe (Williams probe, Hu-Friedy, Chicago, IL, USA) and then if bleeding occurs within 10 seconds, the bleeding sites will be noted as "positive". The number of positive bleeding zones will be divided by the total number of zones present and multiplied by 100 to express the gingival bleeding index as a percentage. Both the plaque index and the gingival bleeding index will be recorded preoperatively and on the 7th and 14th days and 1 month after surgery. The probing pocket depth will be measured by inserting a periodontal probe into the gingival groove until resistance is felt, and the measurements will be recorded to the nearest millimeter. Probing depths will be evaluated for the second molar tooth before surgery and 1 month after surgery. If there is gingival recession in the second molars, the distance between the cement-enamel junction and the free gingival border will be measured at the last follow-up visit.

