### **Statistical Analysis Plan**

Based on previous trial studies, a power analysis was performed using the Power Analysis of Sample Size (PASS) software program, showing that the Standard deviation ( $\sigma$ ) for pain ranged from 4.87 to 5.07. For this reason, the standard deviation was accepted as 5. The effect size was accepted as (d) 2 by the researcher for the 95% confidence coefficient and approximately 80% power value, and the Z value was used as 1.96 for 0.05. type I error rate. Using the sample size calculation equation, the sample size was found to be 24 ( $n = Z^2\sigma^2 / d^2$ ). Descriptive statistics (frequency, mean and standard deviation) were determined for each variable. Kruskal-Wallis H test will be used for comparisons between groups, and Wilcoxon signed rank test will be used for in-group comparisons. All analyzes will be performed using SPSS Version 21.0 (SPSS, Inc., Chicago, IL). A value of  $p < 0.05$  will be considered statistically significant for all analyzes.

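### Two centres with surgeons fixed within each, but no centre stratum in the allocation or in the test: chance centre imbalance between arms is cheap to remove, provided both are changed together

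*Combined protocol and SAP*

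**What the plan says.** The trial "will be conducted in Ankara Yıldırım Beyazıt University Oral and Maxillofacial Surgery Clinic and Van Yüzüncü Yıl University", and "90 healthy individuals who need third molar surgery will be included in this study". The Study Protocol says of the operators: "All procedures will be performed by the same surgeons in each center, using a standard protocol in each medical center". The natural reading is that each clinic has its own surgical team, so surgeon goes with centre.

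Allocation is described once, for everybody: "All patients included will be randomly divided into 3 groups". The method is given as "Randomization will be performed by permutation method in MedCalc 11.5.1 software". The document mentions no stratification by centre, list per centre, block size, recruitment target per centre, or central step by which two clinics would draw from one list in order.

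In the Statistical Analysis Plan, "Kruskal-Wallis H test will be used for comparisons between groups". No centre or surgeon term is mentioned.

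**The concern.** A list that fixes the arm totals over the whole trial does not fix how many patients from each centre fall in each arm. If outcomes differ between centres, because of the operators or of who takes the measurements, an arm with more patients from one centre carries part of that difference. The planned test then reads it as a rinse effect, or lets it mask one. Even when the arms happen to be balanced, variation between centres stays in the error of a test that ignores centre.

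Randomisation covers this on average over repeated trials. At stake are precision and how far the result of this single trial can be separated from centre.

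**Working it through.** **Inputs.** From the documents: 2 centres, 90 patients, 3 arms, SD ("the standard deviation was accepted as 5") and planned difference ("The effect size was accepted as (d) 2 by the researcher for the 95% confidence coefficient and approximately 80% power value"). Assumed: equal allocation (90/3 = 30 per arm), because no ratio is given; centre splits of 45/45 and 60/30, with 72/18 as a further case; SD 5 taken as the SD within a centre.

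**The plan's own figure.** The plan gives no figure for centre balance. Its sample size does reproduce: 1.96² × 5² / 2² = 24.01, stated as 24. It has no bearing on this point beyond supplying the SD and d.

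**Spread of the imbalance under one pooled list.** Let m be the number of patients from one centre. The difference in their count between two arms of 30 has variance 2 × (2/9 + 1/9) × m(90 − m)/89 = (2/3) × m(90 − m)/89.
- m = 45: (2/3) × 45 × 45/89 = 15.17, SD 3.89 patients, 3.89/30 = 13 percentage points.
- m = 60: (2/3) × 60 × 30/89 = 13.48, SD 3.67 patients, 3.67/30 = 12 points.

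**Chance of a large gap** (counts distributed as a multivariate hypergeometric):

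| Centre split | Two given arms differ by ≥ 6 | Largest of the three gaps ≥ 6 | Largest gap ≥ 10 |
|---|---|---|---|
| 45/45 | 16% | 33% | 3.7% |
| 60/30 | 13% | 28% | 2.4% |
| 72/18 | 8% | 17% | 0.5% |

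Blocking the pooled list in threes, sixes or nines leaves these figures almost unchanged. Reading the permutation method as permuted blocks therefore does not help unless the blocks run within centre.

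**Effect on an arm contrast.** Shift = (gap/30) × centre difference D. For a gap of 6 the multiplier is 0.2.
- D = 0: 0.
- D = 2: 0.4.
- D = 5: 1.0.

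For comparison, the standard error of a difference between two arms is 5 × √(2/30) = 1.29.

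**Loss of precision when centre is ignored** (45/45). Total variance = 25 + D²/4.
- D = 2: 26, relative efficiency 25/26 = 0.96.
- D = 5: 31.25, relative efficiency 25/31.25 = 0.80.

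**What each change does.** Simulation with 45/45 centres, 30 per arm, SD 5 within centre, D = 5, and one arm shifted by d:

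| Allocation and test | Type I error | Power at d = 2 |
|---|---|---|
| Pooled list, Kruskal-Wallis | about 5% | 25% |
| List per centre, Kruskal-Wallis | 2.2% | 21% |
| List per centre, centre-stratified rank test | about 5% | 31% |

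With the pooled list and D = 5, the 5% is an average. Among allocations whose largest gap is 6 or more, the Kruskal-Wallis test rejects a true null in about 8% of trials.

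That power is low in every row is a separate matter of sample size.

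**The case against.** **The text does not say that there is one list.** This stands. A separate list at each clinic is compatible with the wording. One pooled list is the plain reading of a single allocation described for all patients with no strata named, but it remains a reading. If lists per centre exist, the protocol should say so, and the pooled test then becomes the problem.

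**Unstratified randomisation is valid.** This stands too. A reader might infer that the comparison is biased or the type I error rate inflated. Neither follows: the imbalance is due to chance and the overall error rate holds.

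**No centre effect is documented.** A reader might infer that surgical technique is known to differ, or that the result is likely to move by half the planned effect. The documents support neither. They describe one procedure for both sites, and the eligibility criteria narrow the case mix. The choice between bone removal and tooth sectioning reads as a decision per case, not as a centre difference. A shift of 1.0 needs both a 20-point gap and a centre difference of one full SD, and it is still smaller than the standard error of 1.29. The wording on surgeons is also loose. If the same people operated at both sites, surgeon mix would matter less, though centre mix would remain.

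**A list per centre alone could do harm.** Correct, as the second row of the last table shows. It determines the form of the fix, but does not remove the reason for one.

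**Conclusion.** The point holds as a cheap improvement. On the plain reading, centre is handled neither in the allocation nor in the analysis. A gap of 6 or more patients between arms would then arise in about 28% to 33% of allocations for centre splits between 60/30 and 45/45, and in about 17% at 72/18. The consequence is 0.2 times an unknown centre difference for each 20-point gap, plus a loss of efficiency of about 4% (D = 2) to 20% (D = 5). If the centres do not differ, nothing is lost.

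These figures rest on one pooled list, 30 patients per arm, and assumed centre splits and differences that the documents do not give. They do not show that the trial is biased, nor that surgeon and rinse are confounded in fact.

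**What to change.** Make both changes together.

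1. **Study Protocol, randomisation.** State that a separate 1:1:1 permuted-block list is generated in MedCalc for each centre, with the block size, and that each centre allocates only from its own list in order of enrolment. With blocks of six, arms within a centre differ by at most 2 patients (2/30, about 7 points).
2. **Statistical Analysis Plan, between-group comparison.** Replace the pooled Kruskal-Wallis test with a rank test stratified by centre (van Elteren type, extended to three groups). The in-group Wilcoxon tests do not compare arms and need no change on this account.

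If lists per centre are already in use, the first change only documents them; the second is still needed.

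Cost: one more run of the same software, a sentence or two in each section, and slightly more analysis work. No extra patients are needed. Each list may end in an incomplete block, so arms could finish one or two patients away from 30. If there is no centre effect, power changes negligibly. The list change must be made before allocation begins.

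### The only allocation coding described is one group number per arm, so a single learned rinse can unmask everyone sharing that number; patient-specific numbers would close this route

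*Combined protocol and SAP*

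**What the plan says.** The Study Protocol opens with the claim of blinding: "This randomized double-blind clinical trial will be conducted". It does not list which parties are blinded.

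The randomisation paragraph describes how the rinses reach the clinic. One sentence, split by a page break, begins "Three types of mouthwash will be given to the clinicians without notifying the surgical procedure or" and continues "postoperative controls, which are individually placed in boxes by the assistant personnel categorized as group 1, group 2 and group 3". Three categories for three arms is a code at arm level. The Study Protocol and the Statistical Analysis Plan describe no patient-specific number, no restricted list linking numbers to rinses, no identical containers and no matching of the products.

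The same paragraph numbers the arms by product: "Extra virgin olive oil will be given to the patients in the second group, and the mouthwash containing chlorhexidine gluconate and benzylamine hydrochloride", the latter for the third group. That leaves St. John's wort oil for the first.

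Two other statements bear on blinding. The periodontal paragraph assigns all periodontal assessments to a blind examiner, without saying how the examiner is kept blind. The non-notification clause in the box sentence appears to mean that those who operate and those who run follow-up are not told the contents.

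For the hand measurements, the plan says "The maximum mouth opening (MMO) will be measured in millimeters with a caliper" and "Facial swelling will be assessed using a thread and a millimeter ruler and five additional measurements will be made". Both are assessed on postoperative days 1, 3 and 7. Who takes them is not stated. Pain, jaw function and painkiller counts come from the patient's own diary.

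**The concern.** With an arm-level code, one lapse does not stay with one patient. If a clinician learns what one patient in group 2 is using, through a remark, a smell or a spilt bottle, the contents of every group 2 box are known from then on. The clinic staff are stable ("All procedures will be performed by the same surgeons in each center"), so the knowledge can carry over to later patients.

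The outcomes most open to this are mouth opening by caliper and the five facial distances by thread and ruler. They depend on the examiner's hand and eye, and no blinded assessor is named for them. If the measurer knows the code, the readings can be influenced and the assessor blinding that the plan seems to intend is weakened.

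There is also a separate route that does not involve the label. Two arms are oils and the control is not, and patients are told to "rinse their mouths with 15 ml of mouthwash 3 times a day for 30 seconds". If they can tell an oil from a non-oil rinse, their pain, jaw-function and analgesic entries may be influenced in the oil-versus-control comparison. The report would then claim a double-blind that the described procedure does not secure.

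**Working it through.** The plan gives no figure on blinding, so there is none to reproduce. The check counts how many patients one learned code exposes.

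**Inputs**
- Total sample: 90 (Study Protocol, eligibility paragraph).
- Arms: 3, with box categories group 1, 2 and 3 (randomisation paragraph).
- Allocation ratio: not stated. Assumed 1:1:1.
- Centres: 2 (opening paragraph). The split is not stated; an equal split is assumed where used.
- Randomisation: a permutation method, with block size not stated.
- Hand measurements: 1 mouth opening and 5 facial distances on 3 postoperative days.

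**Step 1. Arm-level code.** Patients sharing one code: 90/3 = 30. One learned code exposes 30 of 90 (33%). For the other 90 − 30 = 60, the possible rinses fall from three to two. Two learned codes expose all 90. If the arms are unequal, the exposure is the size of the arm whose code was learned.

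**Step 2. One centre only.** If the knowledge stays in one of two equal centres: 30/2 = 15 of 90/2 = 45 patients.

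**Step 3. The non-oil code.** Learning this code alone sorts everyone into oil or control: 30 control + 60 oil = 90 of 90, or 15 + 30 = 45 of 45 in one centre.

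**Step 4. Patient-specific number.** One learned label exposes 1 of 90 (1.1%).

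**Step 5. What blocks leave open.** Suppose permuted blocks of size b are used, with b/3 patients per arm, and staff know the block boundaries. Knowing one patient's rinse then gives, for each block-mate:
- probability of the same arm = (b/3 − 1)/(b − 1)
- probability of each other arm = (b/3)/(b − 1)

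| b | Same arm | Each other arm |
|---|---|---|
| 3 | 0/2 = 0 | 1/2 = 0.5 |
| 6 | 1/5 = 0.2 | 2/5 = 0.4 |

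So the contrast of 30 against 1 is exact for the label alone. Known small blocks would still partly inform staff about a few block-mates, which is much less than certainty about a whole arm.

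**Step 6. Measurements per exposed patient.** (1 + 5) × 3 = 18 postoperative readings. The preoperative set adds 6, giving 24.

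These are counts of exposure. They do not measure bias.

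**The case against.** The strongest reply is that the plan says more about blinding than the box codes. It names a blind periodontal examiner, and the garbled clause most plausibly means that surgeons and follow-up staff are not told what is in the boxes, which would cover the day 1, 3 and 7 visits. This stands. A reader might infer that the codes are the whole of the blinding, or that the swelling and trismus assessors are unblinded. The documents support neither: they do not say who measures, or whether that person sees a code.

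The wording can also be read another way. The boxes may be one per patient, and the categories may describe how the assistants sort them rather than a label the clinician sees. This also stands, and the exposure is therefore conditional on the code being visible. It does not remove the point, because under either reading the only categories stated are one per arm.

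Three further inferences go too far:
- *The box numbers follow the order in which the arms are listed, so the protocol itself decodes them.* The text does not say whether the numbers were scrambled.
- *A third of all hand measurements are compromised.* 18 × 30 = 540 of 18 × 90 = 1,620 counts postoperative readings only. It also needs 1:1:1 allocation, one code common to both centres, staff who share it, and knowledge from the first patient on. No leak is documented.
- *Patient-specific numbers would secure the double-blind.* If an oil is recognisable, patients can learn or disclose oil-versus-control status whatever the box says.

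Finally, that patients can tell the rinses apart is an inference from the product names. Look, taste and feel are not described.

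**Conclusion.** The point holds in conditional form. The claimed double-blind is supported by a blind periodontal examiner, a clause whose meaning must be guessed, and a coding scheme at arm level. If clinicians or assessors see the group code, one learned rinse reveals the rinse of 30 of 90 patients, assuming 1:1:1 allocation, or of 15 of 45 if the knowledge stays in one of two equal centres. A patient-specific label would reveal one.

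The outcomes exposed through the label are mouth opening and facial swelling. The documents do not establish that any assessor is unblinded, and no bias can be quantified from them. The plan should still be changed, because the alternative is better and cheap. Confidence is medium, since whether the code is visible and who takes the measurements are not documented.

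**What to change.** 1. Have the assistant who already packs the boxes label each with a patient-specific randomisation number, in identical opaque containers with no group number. The clinicians can go on handing them out.
2. Keep the list linking numbers to rinses from anyone who operates on or assesses patients.
3. Rewrite the box sentence in the randomisation paragraph to state who is kept unaware, naming whoever measures mouth opening and swelling on days 1, 3 and 7.
4. Unless matching of the rinses is documented, do not claim patient blinding for oil versus control, and interpret patient-reported pain, jaw function and analgesic count in that comparison accordingly.

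Steps 1 to 3 close the label route only. Step 4 limits what the trial concludes and does not remove recognition by patients or staff.

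The cost is slightly more packing work (90 numbered boxes instead of three categories), one list to hold, and a less favourable description of the blinding. No visit is added.

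### If the first 24 hours are rinse-free, should the analgesic count leave out the first day?

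*Combined protocol and SAP*

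**What the plan says.** All the relevant text is in the combined protocol and SAP.

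- **Study Protocol, postoperative instructions:** "Patients will be instructed to maintain a gentle diet for the first 24 hours and to avoid mouthwashing, brushing, and flossing". The next sentence asks patients to "rinse their mouths with 15 ml of mouthwash 3 times a day for 30 seconds and continue until the 7th day after surgery". It gives an end but no start, and does not say whether the study rinse is exempt from the avoidance.
- **Study Protocol, analgesia:** paracetamol is taken as needed, "with a maximum of 4 doses per day after surgery".
- **Study Protocol, outcomes:** one outcome is "the number of analgesics used in the first postoperative week". The diary runs for seven days, and for painkillers the instruction is "They will also be asked to note how many painkillers they take per day". Clinic assessments cover "swelling and trismus on postoperative 1st, 3rd and 7th days".
- **Statistical Analysis Plan:** "Kruskal-Wallis H test will be used for comparisons between groups". It does not say whether the daily counts are summed first or compared day by day.

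Neither section says whether the first diary day is the day of surgery or the day after.

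**The concern.** The two rinse sentences fit together most naturally as a sequence: no rinsing for 24 hours, then rinsing to day 7. On that reading no mouthwash can affect analgesic use in the first 24 hours, yet that use sits inside the weekly count.

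A day without exposure leaves the expected group difference unchanged and adds its own variance, plus its covariance with later days. The test on the total is then weaker than a test on days 2 to 7, unless first-day use is negatively correlated with later use. Because the diary is kept by day, the shorter count would need no new data.

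Day-1 swelling and trismus raise a related point. If that visit comes before the first rinse, a null result there says nothing about the mouthwashes.

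What would be at stake is power for one outcome and the reading of one visit. All three groups get the same instructions, so neither bias nor type I error is in question.

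**Working it through.** **The plan's own figure.** The SAP's sample size reproduces: 1.96² × 5² / 2² = 3.8416 × 25 / 4 = 24.01, stated as 24. Its inputs (SD 5, difference 2) are for pain, and the formula has no power term. It tells us nothing about the analgesic count, so everything below rests on assumptions.

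**Variance ratio.** Assume the first diary day carries no effect, days 2 to 7 have a common SD, the first-day SD is *k* times that, and any two days have correlation *r*. Then

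R = Var(days 1–7) / Var(days 2–7) = 1 + (k² + 12kr) / [6(1 + 5r)].

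With k = 1 this is 7(1 + 6r) / [6(1 + 5r)], or 1.167 at r = 0 and 1.361 at r = 1.

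**Power.** For three groups (2 df, alpha 0.05), a noncentrality of 9.635 gives 80%. Dividing it by R gives the power of the total when the days 2–7 count has 80%:

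| First-day SD relative to later days | R (r = 0 to 1) | Power of total | Loss from 80% |
|---|---|---|---|
| half | 1.04–1.17 | 78.3–72.9% | 2–7 points |
| equal | 1.17–1.36 | 73.2–66.1% | 7–14 points |
| double | 1.67–1.78 | 56.7–53.8% | 23–26 points |

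With an equal split of the 90 patients (assumed, since the ratio is not stated), the middle row makes 30 per group worth 30/1.167 = 25.7 down to 30/1.361 = 22.0.

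**Steeper assumptions.** If the daily SD falls 30% a day, R is 2.06 to 2.19 for r from 0 to 0.7. In a two-group normal approximation, power is Φ(2.80/√R − 1.96), which is 50% to 47%, a loss of 30 to 33 points.

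**Lower starting power.** The 80% is imposed. If the pain ratio 2/5 is borrowed with 30 per group and one arm differing, the noncentrality is 30 × 0.4² × 2/3 = 3.2 and power is 34%. Dividing by 1.167 and 1.361 gives 30% and 26%, a loss of 4 to 8 points.

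**Kruskal-Wallis simulation.** This used three groups of 30, binomial counts of 0 to 4 a day, correlation 0.3 to 0.7, and an effect on days 2–7 only, tuned to about 80% power for that count.

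| Assumed use over the week | Days 2–7 count | First-week total | Loss (points) |
|---|---|---|---|
| level, 1.5 a day | 77.5–78.3% | 64.0–64.6% | 12.9–14.3 |
| declining from 3 to 0.5 | 76.9–78.7% | 64.0–64.8% | 12.4–14.7 |
| steep decline from 3 to 0.1 | 77.4–78.6% | 51.4–57.6% | 20.8–26.0 |

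Losses above 15 points appear only under the steep decline. The null rejection rate was 4.6 to 5.1%.

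**If the premise changes.**

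- With the full effect present on the first day, the total reaches 79% (level), 89–90% (declining) or 96–97% (steep). Leaving that day out then costs 1 to 19 points.
- With half the effect on the first day, keeping it changes power by −6 to +7 points.
- If days are compared separately, days 2 to 7 are not diluted at all.

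**The case for a change.** The strongest case for changing the plan is that the mechanism is certain once its premises are granted. A summed count with an unexposed day is less efficient, the diary already holds the alternative, and swapping one count for the other adds no test. The sequential reading of the rinse instructions is the natural one, and the outcome's wording does suggest a single weekly figure. All of this stands as far as it goes.

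It falls short of requiring a change for three reasons.

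- Two premises are not in the documents: that the first diary day coincides with the rinse-free 24 hours, and that the seven days are summed before testing. If the first diary day is the day after surgery, it is partly or wholly exposed, and the case for dropping it goes.
- Any gain depends on the missing start time. On the other reading, the same change loses power.
- The two counts answer different questions. Analgesic use from surgery through day 7 describes what the patient goes through under the whole regimen, including any delayed start. Days 2 to 7 describes use while rinsing. Efficiency alone does not make the declared outcome wrong.

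**Conclusion.** No change to the analysis plan follows. The first-week analgesic count is a fair outcome, and the choice between it and a days 2–7 count is a trade-off on which statisticians could reasonably differ.

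The possible loss is real but conditional. It is about 2 to 26 points at an assumed 80% power for first-day SDs of half to twice the later SD, and past 30 points only if variability falls steeply over the week. It is about 4 to 8 points at 34% power, and zero if days are analysed separately. These figures assume an equal split of 90, no effect on the first diary day, non-negative correlation between days, and summation of the seven counts. No figure in the documents fixes any point in that range. The consequence is also limited: analgesic use is one of several outcomes with no named primary, and the day-3 and day-7 swelling and trismus comparisons are untouched.

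What remains is missing detail that the authors can supply before unblinding: reconcile the two rinse sentences, say which day the first diary day is, and say how the daily counts are handled. Analysts can then read day-1 swelling and trismus accordingly. If the first diary day proves rinse-free, they can show a days 2–7 count as supportive beside the declared total. Nothing here implies when rinsing should start.

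### The trismus percentage has two divisors in one sentence: the words point to the preoperative mouth opening, the printed formula uses the postoperative one

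*Combined protocol and SAP*

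**What the plan says.** The Study Protocol lists trismus among the outcomes: "The outcome variable will be patient-reported pain and difficulty in jaw function, trismus, facial swelling". Its raw measurement is set out in the section's procedures: "The maximum mouth opening (MMO) will be measured in millimeters with a caliper". Trismus is then expressed as a percentage difference, with the preoperative opening labelled A and the postoperative opening labelled B. In words, the analyst is to "subtract the preoperative measurement (A) from the postoperative measurement, and then divide the preoperative measurement (A) and multiply by 100". The bracket that closes the same sentence gives the formula as [B - A]/B x 100.

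A few lines later the percentage of facial swelling is defined by "subtracting the preoperative measurement from the postoperative measurement and then dividing it by the preoperative measurement and multiplying by 100". Both outcomes are assessed together: "swelling and trismus on postoperative 1st, 3rd and 7th days".

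The Statistical Analysis Plan says of the summaries: "Descriptive statistics (frequency, mean and standard deviation) were determined for each variable". For testing it says "Kruskal-Wallis H test will be used for comparisons between groups" and "Wilcoxon signed rank test will be used for in-group comparisons". It does not define the trismus percentage again, and it does not say whether the tests use percentages or millimetres.

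**The concern.** The words and the formula cannot both be followed. The only quantity the words name in the division step is A, whereas the formula divides by B. The two give different values for every patient whose mouth opening changes.

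A formula is what usually gets coded. An analyst who follows the bracket would report percentage losses larger than the words describe, on a scale with no lower limit, and on a different base from facial swelling, which is described in parallel. What is at stake is the reported size of a named outcome: its means, its SDs and the differences between group means. Tests are affected only in some circumstances, set out below.

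**Working it through.** There is no trismus figure in the documents to reproduce, so the check compares the two definitions.

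**Inputs.** A is the preoperative and B the postoperative opening (Study Protocol). The documents give no mouth-opening data. A = 45 mm and all B values below are assumptions for illustration.

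**Exact relation.** Dividing one version by the other, {[B - A]/B} / {[B - A]/A} = A/B. Losses (B < A) are inflated and gains (B > A) are shrunk. The printed version passes -100% once B is below A/2.

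| B (mm), A = 45 | [B - A]/A x 100 | [B - A]/B x 100 | A/B |
|---|---|---|---|
| 40.5 | -10.0 | -11.1 | 1.11 |
| 36 | -20.0 | -25.0 | 1.25 |
| 31.5 | -30.0 | -42.9 | 1.43 |
| 27 | -40.0 | -66.7 | 1.67 |
| 22.5 | -50.0 | -100.0 | 2.00 |
| 18 | -60.0 | -150.0 | 2.50 |

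**Group means, without assuming a distribution.** Let r = B/A. The mean loss with divisor A is L = 1 - mean(r). With divisor B it is mean(1/r) - 1. By Jensen's inequality mean(1/r) is at least 1/mean(r), so the mean loss with divisor B is at least 1/(1 - L) - 1 = L/(1 - L):

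- L = 20%: at least 0.20/0.80 = 25.0%
- L = 30%: at least 0.30/0.70 = 42.9%
- L = 40%: at least 0.40/0.60 = 66.7%

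**SDs and group differences (illustration only).** Take two groups of three patients, each with A = 45 mm.

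| Group, B (mm) | Divisor A: mean (SD) | Divisor B: mean (SD) |
|---|---|---|
| 40.5, 36, 31.5 | -20.0 (10.0) | -26.3 (15.9) |
| 36, 31.5, 27 | -30.0 (10.0) | -44.8 (20.9) |

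The difference in means is 10.0 points with divisor A and 44.8 - 26.3 = 18.5 with divisor B. The SDs are equal with divisor A and unequal with divisor B.

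**Kruskal-Wallis at one visit.** With divisor A the percentage is 100(r - 1). With divisor B it is 100(1 - 1/r). Both rise with r, so all ranks, and therefore H and p, are identical. In a simulated set of three groups of 30, H = 11.973 and p = 0.0025 under both versions.

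**Signed-rank within a group.** This test ranks the absolute differences, so a change in scale can matter.

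- *Against baseline, with some B > A:* r = 0.90 and 1.105 give -10.0 and +10.5 with divisor A, but -11.1 and +9.5 with divisor B. The positive rank sum goes from 2 to 1. If nobody exceeds baseline, every non-zero difference is negative under both versions and nothing changes.
- *Between two postoperative days:* one patient going from r = 0.60 to 0.70 and another from 0.95 to 0.83 change by +10.0 and -12.0 with divisor A, but by +23.8 and -15.2 with divisor B. The positive rank sum goes from 1 to 2.

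Tests on the raw millimetres do not depend on the divisor.

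**The case against.** The strongest reply is that this is a typing slip whose intent can be recovered. The words name only A, the swelling rule spells out the preoperative divisor in full, and a careful analyst would probably use A. The letter could also have been misread when the text was extracted from the PDF, and the verbal rule itself lacks a word, so both halves need some interpretation. The slip is indeed the likely explanation. But the text as supplied conflicts, no reading of the words yields division by B, and no other section settles it.

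The second reply is that little inference depends on it. The between-group test at each visit is unchanged. The within-group effect requires that the signed-rank tests use percentages, which the Statistical Analysis Plan does not state, and, for comparisons with baseline, that some patients open wider than before surgery. The two-patient examples show that ranks can move, not that a significance decision would. Trismus is one of several outcomes, and the sample size rests on pain. All of this stands, and it limits the point to the descriptive results and possibly some within-group tests.

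The third reply is that the 18.5-point figure comes from invented groups. That is correct: it shows the direction of the effect and is not a forecast for this trial. The factor A/B and the bound L/(1 - L) are exact and do not depend on those groups.

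**Conclusion.** The contradiction holds as a minor error in an outcome definition. If the printed formula is coded, each patient's percentage is multiplied by A/B relative to the rule in words, and a mean loss L is reported as at least L/(1 - L). Trismus means, SDs and differences between group means would then not be on the scale the words describe. Single-visit Kruskal-Wallis results and any test on millimetres are unaffected, while signed-rank tests on percentages may change.

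The conclusion that A is the intended divisor rests on supplying the missing 'by' and on the parallel swelling rule. Confidence that the text conflicts is high. That the source formula contains a slip is likely, and the sponsor can confirm it quickly.

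**What to change.** Correct the printed formula to [B - A]/A x 100 and restore 'by' before the preoperative measurement in the sentence, after the sponsor confirms that this was the intent. Use that version in the analysis code and in every trismus summary.

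The cost is one letter, one word and a check of one line of code. No new data are needed: mouth opening is recorded in millimetres, so percentages already computed the other way can be redone.
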